- a HAAH assessment: following informed consent, archived prostate tumor tissue and patient serum will be tested for the expression of HAAH. Only patients who test positive for HAAH expression in archived tumor tissue (if available) or fresh serum may be continued in the study. HAAH assessments are not subject to the 56-day screening window and are valid for 6 months. Patients who are negative for HAAH may be followed for 6 months and if PSA rises over that period time, they can enroll in the study provided that tissue or fresh serum is positive for HAAH
- b Biochemical testing (chemistry, complete blood count, coagulation, and total complement CH50,) to be obtained within 14 days prior to study drug administration if screening period is between 3 and 8 weeks. PSA levels are also to be evaluated at screening and within 14 days prior to study drug administration if screening period is between 3 and 8 weeks.
- c Immunologic blood collection: to be taken pre-dose on the day of study drug administration (Day 1) and every 21 days thereafter. Following the 9th dose (or last dose otherwise), PSA levels and other assessments will be followed on a monthly basis for 6 months. Patients with evidence of progression and declining HAAH immune parameters will have the option of resuming therapy on the study protocol.

- d Baseline radiological tumor burden evaluation consists of a baseline pelvic MRI or CT scan in addition to bone scan. These studies will need to be performed within 56 days (+ 7 days) prior to the start of the study.
- e Patients that have a delay in screening beyond 56-days may be re-screened for randomization.
- f Adverse events that occur post patient receiving study drug. Should Adverse event occur prior to patient receiving study drug they will be captured as Medical History.

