5.2 Selection of Study Population

5.2.1 Inclusion Criteria

- 1. Signed and dated written Ethics Committee approved informed consent
- 2. Men aged 21 to 85 years with a histologic diagnosis of prostate cancer with a biochemical relapse following definitive local therapy (RP or radiation therapy)
- 3. Patients are not eligible or are unwilling to receive additional definitive therapy following relapse (either RP or radiation therapy)
- 4. No prior cytotoxic chemotherapy for the current cancer
- 5. Normal electrocardiogram (ECG) or ECG with no clinically significant findings as determined by the Principal Investigator
- 6. Presence of biochemically relapsed prostate cancer defined as either: 1) PSA > 2 ng/mL 1 year following initial definitive treatment for prostate cancer: or, 2) PSA doubling time (greater than 0.2 ng/mL) < 12 months; or, 3) PSA velocity > 2 ng/mL/year at any time following radical prostatectomy or radiation therapy.
- 7. Positive expression of HAAH in either archived tumor tissue (if available) or fresh serum
- 8. No clinical or radiologic evidence of distant metastatic disease as measured by pelvic MRI or CT scan in addition to bone scan. These studies will need to be performed within 56 (+ 7 days) days prior to the start of the study.
- 9. No history of immunosuppressive disease
- 10. No evidence of active autoimmune disease. Active autoimmune disease is defined as any disease process that has specifically needed administration of immune suppressive and or cytoreductive therapy currently or within the last 1 year.
- 11. Able and willing to comply with all study procedures

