6.4 Secondary Endpoints

- Incidence of administration site reactions
- Biochemical safety and tolerability (hematology, serum chemistry, coagulation, CH50)
- Geometric mean titers of anti-HAAH antibodies by dose
- Antigen-specific Cytotoxic CD8+ T-lymphocytes (CTL) responses by dose
- Production of B cell and T cell response of interest

Clinical Secondary Endpoints:

- Change in the prostate-specific antigen (PSA) velocity
- Reduction in the PSA doubling time from pre-baseline

Pharmacodynamic Secondary Endpoints:

- Duration of antigen-specific anti-HAAH antibody titers
- Changes in the amplitude or duration of the production of anti-HAAH antibodies
- Correlation of anti-HAAH titers and serum HAAH levels

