7.4 Analysis of the Study

All statistical tests will be two-sided and a difference resulting in a p-value of less than or equal to 0.05 will be considered statistically significant. All p-values will be rounded to and displayed in four decimals. If a p-value less than 0.0001 occurs it will be shown in tables as <0.0001.

There will be no multiplicity adjustments.

Descriptive summaries of variables will be provided where appropriate. For continuous variables, the number of non-missing values (n) and the median, mean, standard deviation, minimum, and maximum will be tabulated by dosage group. For categorical variables, the counts and proportions of each value will be tabulated by dosage group. Since this study allows for subjects to change their dose level during additional treatment visits after Day 43, the dose level can change over the course of the study; see Section 8 for how summaries by dosage group will be handled when dose levels vary.

Expansion of descriptive table categories within each treatment may occur if such elaborations are thought to be useful.

Assessments completed during the 6-month follow up period after study treatment will not appear in any tables or graphs (unless noted otherwise), but will be included in the data listings, classified under the last dose level the subject took at the last treatment visit prior to the end of study.

All collected data will be presented in listings. Data not subject to analysis according to this plan will not appear in any tables or graphs but will be included in the data listings.

Post-hoc exploratory analyses not identified in this SAP may be performed to further examine the study data. These analyses will be clearly identified as such in the final clinical study report.

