8.5 Clinical Analysis

PSA will be summarized descriptively for each dosage group by visit for the observed value as well as for the change from baseline value (Day 1). Subjects will be summarized through Day 43 using the assigned dose level as the treatment group. For additional treatment visits, follow up visits, and end of study, subjects will be summarized by cohort and by the dose level the subject took at the visit immediately prior to the current visit—this allows for subjects who changed their dose level to be summarized at the new dose level.

PSA velocity (ng/mL/year) will be estimated by the slope of the least-square regression line fit to PSA versus time in years [1]. PSA velocity will be calculated using PSA values between Day 1 and Day 43, and subjects will be summarized using the assigned dose level as the treatment group. Also, to account for additional treatment visits, PSA velocity will be calculated using PSA values between Day 1 and the end of treatment phase visit, and subjects will be summarized by cohort and by the dose level the subject took at the last additional treatment visit. Finally, to account for follow up visits, PSA velocity will be calculated using PSA values between Day 1 and the end of study visit, and subjects will be summarized by cohort and by the dose level the subject took at the last treatment visit prior to the end of study.

PSA doubling time (months) will be estimated as follows for each visit range [1]:

- 1) Calculate the natural log-transform of all PSA observations [log(PSA)] in the visit range
- 2) Determine the slope of the least-square regression line of log(PSA) versus time in months of PSA measurement; convert the slope from years to months by multiplying the slope in years by the factor 12.
- 3) Divide the natural log of 2 [log(2)] by the slope calculated in step 2.

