PSA doubling time will be estimated for 3 visit ranges: 1) up to and including Day 1 (baseline); 2) Day 1 through Day 43; 3) Day 1 through end of treatment phase visit; and 4) Day 1 through end of study. The baseline value will use all PSA values collected in the Medical History eCRF as well as any screening or Day 1 values in the safety laboratory data extract. For each post-baseline date range, each subject's PSA doubling time will be compared to their baseline value, and the number of subjects who have improved in the parameter (longer or negative doubling time) will be summarized, as well as the number of subjects who have not improved or who are worse (no change or shorter doubling time). For the summary from Day 1 through Day 43, subjects will be summarized using the assigned dose level as the treatment group. For Day 1 through end of treatment phase visit, subjects will be summarized by cohort and by the dose level the subject took at the last additional treatment visit and for Day 1 through end of study, subjects will be summarized by cohort and by the dose level the subject took at the last additional treatment visit and for Day 1 through end of study, subjects will be summarized by cohort and by the dose level the subject took at the last additional treatment visit and for Day 1 through end of study.

All PSA analyses will be conducted on the Safety Population.

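### SAP 8.5 fits the baseline PSA doubling time to every PSA value on the Medical History form, with no post-nadir start, and compares doubling times in a way that breaks down when the baseline is negative

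*SAP*

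**What the plan says.** SAP 6.4 lists "Reduction in the PSA doubling time from pre-baseline" as a clinical secondary endpoint. SAP 8.5 estimates PSADT in each visit range by regressing log PSA on time and dividing log 2 by the slope. The first step is: "Calculate the natural log-transform of all PSA observations [log(PSA)] in the visit range". The baseline range is open on the left and ends at Day 1: "The baseline value will use all PSA values collected in the Medical History eCRF as well as any screening or Day 1 values". Each post-baseline PSADT is then compared with the patient's own baseline, and "the number of subjects who have improved in the parameter (longer or negative doubling time) will be summarized"; no change or a shorter time counts as not improved or worse.

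SAP 8.5 gives no starting point for the baseline window, no PSA floor and no minimum number of values. It mentions a negative doubling time only as a form of improvement, so it has no specific rule for a negative baseline. SAP 7.4.10 defines a single-value baseline and does not fill these gaps.

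Protocol 5.2.1 requires relapse after prostatectomy or radiation (criterion 2). One route into criterion 6 is "PSA velocity > 2 ng/mL/year at any time following radical prostatectomy or radiation therapy". Another is a PSADT qualified by PSA above 0.2 ng/mL, a qualifier that SAP 8.5 does not carry over. Before treatment the schedule provides for screening and Day 1 PSA. Footnote b to the Time and Events Schedule adds, for screening periods of 3 to 8 weeks: "PSA levels are also to be evaluated at screening and within 14 days prior to study drug administration".

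**The concern.** One log-linear line through a fall and a later rise does not estimate growth during relapse. If the history form contains a value from before definitive therapy, or a nadir that lies off the relapse trend, the baseline slope can be flattened, steepened or reversed. Every later PSADT for that patient is judged against it.

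The second problem does not depend on what the form holds. PSADT is a reciprocal of the slope and jumps from large positive to large negative as the slope passes through zero. With a negative baseline, any positive post-baseline PSADT is numerically longer, and any negative one counts as improved by rule. Read literally, such a patient cannot be scored worse.

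At stake is the improved versus not-improved count for a named secondary endpoint in about 18 patients split by dose, where a few misclassified patients change the table.

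**Working it through.** The documents state no PSADT value or expected effect for this endpoint, so there is no figure to reproduce. The check applies the SAP's own algorithm to assumed histories.

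**Inputs.** From SAP 8.5: s = least-squares slope of ln(PSA) on months, and PSADT = ln 2 / s = 0.69315 / s. Assumed: Day 1 PSA of 3 ng/mL; exact exponential growth through relapse values at months -24, -18, -12, -9, -6, -3, -1 and 0; a pre-surgery PSA of 8 at month -60; a nadir of 0.05 at month -57.

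**Step 1: baseline PSADT in months (slope per month in brackets).**

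| Values in the fit | True 6 | True 9 | True 12 |
|---|---|---|---|
| Relapse only | 6.0 (0.11552) | 9.0 (0.07702) | 12.0 (0.05776) |
| + nadir | 9.4 (0.07383) | 9.6 (0.07207) | 9.7 (0.07119) |
| + pre-surgery and nadir | 33.8 (0.02050) | 31.0 (0.02239) | 29.7 (0.02333) |
| + pre-surgery only | -57.7 (-0.01201) | -52.2 (-0.01328) | -49.8 (-0.01391) |

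**Step 2: why the nadir works both ways.** At month -57 the relapse line stands at 3 × 2^(-57/T) for true PSADT T: 0.004 for T = 6, 0.037 for T = 9 and 0.111 for T = 12. A nadir of 0.05 lies above the first (flattens the slope), close to the second (almost no effect) and below the third (steepens it). A nadir on the line does no harm: at T = 6 that is month -6 × log2(3/0.05) = -35.4, and the fit still returns 6.0.

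In a nadir-only grid of 4 × 3 × 4 = 48 histories (Day 1 PSA 2, 3, 5, 10; nadir 0.02, 0.05, 0.1; nadir at month -45, -57, -81, -117), the baseline came out too short in 3 histories at true PSADT 6, 17 at 9 and 27 at 12.

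**Step 3: effect on the label, without noise.**
- Growth truly halves, PSADT 6 to 12, baseline 33.8: 12 < 33.8, so a real slowing is scored worse.
- No true change, PSADT 12, baseline 9.7: 12 > 9.7, so no change is scored improved.
- Baseline -57.7, post-baseline 12: literally 12 > -57.7, so improved. On slopes, 0.05776 > -0.01201, so worse.

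**Step 4: effect on the label, with noise.** Simulation of 200,000 patients per cell, log-PSA SD 0.10 (assumed), Day 1 value shared by both fits, post-baseline values at days 0, 21, ..., 168 and 196, growth truly halved. Percentage scored improved through end of treatment:

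| Change in true PSADT | Relapse-only baseline | + nadir |
|---|---|---|
| 6 to 12 | 100% | 84% |
| 9 to 18 | 99% | 98% |
| 12 to 24 | 95% | 99.6% |

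For 6 to 12, adding both the pre-surgery value and the nadir gives 1%. Adding the pre-surgery value alone gives 100% on a literal comparison and 0% on slopes. Over SD 0.05 to 0.15, the 6-to-12 figures are 99-100% (relapse only), 75-98% (nadir) and 0-6% (both).

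**Step 5: which remedy works (true PSADT 6).**
- A 0.2 ng/mL floor alone does not. It drops the nadir and the month -24 value (0.1875) but keeps the pre-surgery value: slope -0.0199, PSADT -34.9.
- After radiation, with a nadir of 0.5 or 0.8 at month -45, the pre-therapy 8 at month -60 and relapse values above the nadir, every value exceeds 0.2. The results are -115 and -83 with or without the floor.
- Starting after the nadir recovers 6.0 in all these cases, on 8, 6 and 5 values.
- The start must follow the last nadir-level value. With flat values of 0.05 at months -57, -48 and -39, starting after the first still gives 7.5.

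**The case against.** The strongest objection is that nothing supplied shows the troublesome values exist. The SAP cites an eCRF dated 07 August 2018 that is not available, and SAP 10.2 places the shells and programming notes in a separate document that could contain a start rule. Criterion 6 speaks of PSA after therapy. It makes early post-therapy values plausible but gives no support for pre-therapy ones, and the largest figures above all need a pre-therapy value. A form that records only relapse-phase PSA is at least as plausible. This stands, and it makes the first half of the point conditional. It does not touch the negative-baseline problem, which lies in the comparison rule itself.

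A reader might infer that the errors fall mostly toward worse and so hide a real slowing of PSA. The documents do not support that. A low nadir can steepen the baseline, and a negative baseline read literally favours improved. Histories limited to nadirs on or above the relapse line would always show flattening, but only because of that restriction; nothing in the documents establishes constant growth.

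A reader might also infer that this count is the only planned comparison with pre-treatment PSA growth. Every PSA velocity window does start at Day 1. But SAP 8.5 also estimates the baseline PSADT itself, Tables 14.2.3.2.1 to 14.2.3.2.3 summarise PSADT, and without the shells their content is unknown.

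Finally, "All collected data will be presented in listings", so a reader could spot an implausible baseline. That is true, but the tabulated count would still carry it.

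**Conclusion.** The point holds in a limited form. As written, SAP 8.5 fits the baseline to whatever PSA history the form contains, in patients whose PSA fell and then rose, and it compares a quantity that is not ordered sensibly across zero. If pre-therapy or off-trend nadir values are collected, misclassification can go either way: toward worse when the slope is flattened but positive, toward improved when it is steepened, and dependent on the reading when it is negative. The effect ranges from trivial (true PSADT 9, nadir only: 9.6) to decisive (true PSADT 6 with pre-surgery and nadir values: 33.8, and 1% instead of 100% scored improved when growth halves).

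The PSA histories, growth rates and noise levels are assumptions, and the content of the eCRF is unknown. The endpoint is descriptive and secondary; MTD and RP2D do not depend on it. This is a cheap improvement of minor to moderate weight.

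**What to change.** 1. Whatever the eCRF contains, classify on log-PSA slopes: improved if the post-baseline slope is lower than the baseline slope, otherwise not improved. For a positive baseline this gives the same label as the present rule, so only patients with a zero or negative baseline are affected. Show each patient's slope difference beside the count.
2. Check the eCRF. If it collects only relapse-phase PSA, say so in SAP 8.5. Otherwise limit the baseline regression to values after the last post-therapy nadir-level value, up to Day 1. Define nadir level numerically, and state a minimum number of values (for example three) with a not-evaluable category below it.

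If pre-therapy values enter the fit, the first step alone is not enough: a slope comparison against a falsely negative baseline would score any rising PSA as not improved.

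The cost is a few sentences of SAP text and modest programming, including a nadir date flag per patient. The downside is that patients with too few post-nadir values leave the comparison. Their number is unknown, because the schedule guarantees only screening and Day 1 PSA plus the retest after a longer screening period. The choice of minimum is a judgement and should be fixed before the PSADT results are reviewed.

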8.6 Safety Analysis

All safety analyses will be conducted on the Safety Population.

Unless otherwise specified, subjects will be summarized through Day 43 using the assigned dose level as the dosage group. For additional treatment visits and end of treatment phase visit, subjects will be summarized by cohort and by the dose level the subject took at the visit immediately prior to the current visit—this allows for subjects who changed their dose level to be summarized at the new (elevated) dose level.

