| | Treatment will consist of single repeated doses of SNS-301 administered every 21 days for 3 doses. A traditional 3+3 dose-escalation schema will be used to determine the MTD of SNS-301 for the first 2 doses and a modified dose-escalation schema for the remaining dose. Planned doses of SNS-301 are 2.0×10^{10} , 1.0×10^{11} and 3.0×10^{11} particles per administration diluted to 1 mL and administered intradermally. Additional patients will be enrolled at the highest dose level until at least 6 patients can be evaluated even if no DLTs are observed at the dose. Planned treatment may continue for two additional doses of SNS-301 administered every 21 days. Serum and whole blood samples will be obtained on the day of study treatment, at Day 1, Day 8, Day 15, and Day 22 during the first cycle. For patients who continue to receive study treatment, biochemical and immunologic testing will continue every 21 days. |
| | The MTD will be determined over the first 21-day interval following a single dose of SNS-301 in 3 dose cohorts. The MTD will be considered the dose level lower than the dose producing \geq 2 DLTs in 3-6 patients. Patients who withdraw in cycle 1 for reasons other than safety or toxicity will be replaced. Any of the following, if judged to be associated with SNS-301 |

| (i.e., possibly-, probably-, or definitely related to), will be considered a DLT using the National Cancer Institute-Common Terminology Criteria for Adverse Events (NCI-CTCAE) Version 4.03: |
|--|
| 1) Grade 4 non-hematological toxicities (excluding alopecia) of any duration |
| Grade 3 non-hematologic (non-laboratory) toxicity lasting > 3 days despite optimal supportive care |
| 3) Any Grade 3 or Grade 4 non-hematologic laboratory value if: a). Medical intervention is required to treat the patient; b), the abnormality leads to hospitalization; c). The abnormality persists for >1 week. |
| 4) Grade 4 hematologic toxicity, other than those specified in criteria 5 and 6 below, lasting > 7 days |
| 5) Grade 3 or Grade 4 febrile neutropenia of any duration |
| 6) Grade 3 thrombocytopenia in combination with a grade 3 or greater blood and lymphatic system disorder |
| 7) Grade 3 AST or ALT that is associated with a grade 2 rise in bilirubin |
| The recommended Phase 2 dose (RP2D) will be defined as the highest dose administered if no MTD is observed. |

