| | Signs and symptoms (bascline): Screening, Day 1 Physical examination: Screening and end of study (EOS) Symptom-directed physical examination: Day 1, Day 8, Day 15, Day 22, Day 43 and if additional treatment is given, at 21-day intervals thereafter Biochemical testing (chemistry, CBC, coagulation, CH50): Screening, Day 1, Day 22, Day 43 and if additional treatment is given at 21-day intervals thereafter and EOS Biochemical testing (chemistry, CBC, coagulation, CH50) Day 8 and Day 15 during cycle 1 Study treatment administration: Day 1, Day 22, Day 43 and if additional treatment is given, at 21-day intervals thereafter for a total of 9 injections. Patients who have received more than 9 injections due to the timing of the amendment that details limiting therapy to 6 months (9 doses), will be stopped at their last dose received and be followed for 6 months as with other patients. Patients with off-treatment evidence of progression and declining HAAH immune parameters during the 6-month observation period will have the option of immediately resuming therapy on study protocol. Physician administration site assessment: Day 1, Day 8, Day 22, Day 43 and if additional treatment is given at 21-day intervals thereafter; and EOS Safety evaluation of subject to permit continued enrollment in each cohort Day 21 for every first and last patient in a dose level Eastern Cooperative Oncology Group (ECOG) performance score: Screening, Day 1, Day 8, Day 15, Day 22, Day 43 and if additional treatment is given, at 21 day intervals thereafter; and EOS Prostate-specific antigen (PSA) assessment: Screening, Day 1, Day 22, Day 43 and if additional treatment is given, at 21 day intervals thereafter; until injection number 9 (or last dose otherwise) and EOS. Afterwards PSA levels will be obtained on a monthly basis for a total of 6 months. Martue olici blood collection: Screening, Day 1, Day 22, Day 43 and if additional treatment is given, at |
|-----------------------|--|
| Statistical analysis: | No formal statistical analysis will be performed, however, statistical derivation of all data will be derived by dose cohort and displayed for inspection. |

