7.4.7 Handling of Early Termination Visits and Additional Treatments

Early termination visit data (on or prior to Day 43) for safety variables will be analyzed at the closest scheduled visit. If the closest visit has valid data, the early termination data will be assigned to the next available visit.

Any safety or immunologic data collected for additional treatments (after Day 43) will be summarized as visits separate from the scheduled visits (up to and including Day 43 and End of Study).

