8.6.1 Administration Site Reactions

Administration Site reactions include local (injection site) reactions, such as pain, tenderness, erythema/redness, and swelling. Events are collected via the Physician Administration Site Assessment eCRF page and are graded using a severity rating of 0 (none), and 1, 2, 3, 4 (mild, moderate, severe, potentially life threatening).

A summary of the number and percentage of subjects experiencing at least one administration site reaction anytime after the first study treatment administration will be tabulated by reaction type, maximum severity, and dosage group through Day 43, and separately, for additional treatment visits after Day 43. A separate summary will be tabulated for each visit that an assessment is scheduled.

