8.6.5 ECOG Performance Score

The health, activity and well-being of the patient is measured by the ECOG performance status and is assessed on a scale of 0 to 5, with 0 being fully active and 5 being dead. The ECOG performance score will be summarized categorically by dosage group and visit. In addition, a shift table will be provided comparing the baseline ECOG

performance score and the worst (highest) post-baseline score that was recorded through Day 43.

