8.6.6 ECG

ECG results will be summarized descriptively for each parameter and dosage group by visit for the observed value as well as for the change from baseline value. In addition, a shift table will be provided comparing the baseline overall interpretation (normal, abnormal, not clinically significant, abnormal, clinically significant) to the post-baseline value by visit through Day 43.

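### The SAP's assigned-dose safety period ends on the day of dose 3, which splits off later dose 3 events, leaves three-dose patients without a clear adverse-event table, and truncates the ECOG and ECG shifts

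*SAP*

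**What the plan says.** The protocol synopsis describes an initial three-dose course: "Treatment will consist of single repeated doses of SNS-301 administered every 21 days for 3 doses". Its list of evaluations gives the days: "Study treatment administration: Day 1, Day 22, Day 43 and if additional treatment is given, at 21-day intervals thereafter". Day 43 is therefore the day of dose 3.

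SAP 8.6 sets the safety default that "subjects will be summarized through Day 43 using the assigned dose level as the dosage group". The second period is defined by "For additional treatment visits and end of treatment phase visit, subjects will be summarized by cohort" and by the dose taken at the preceding visit. SAP 7.4.7 adds: "Any safety or immunologic data collected for additional treatments (after Day 43) will be summarized as visits separate from the scheduled visits". SAP 8.6.1 tabulates administration site reactions by "dosage group through Day 43, and separately, for additional treatment visits after Day 43". The reason for a split is in SAP 7.4: a patient's dose level may change at additional treatment visits after Day 43.

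For ECOG, SAP 8.6.5 compares baseline with "the worst (highest) post-baseline score that was recorded through Day 43". For ECG, SAP 8.6.6 compares the baseline interpretation "to the post-baseline value by visit through Day 43". In SAP 10.1 the adverse-event tables come in pairs, one through Day 43 and one for additional treatment visits.

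**The concern.** A cut on the day of dose 3 gives the first two doses a full observation interval in the assigned-dose tables and gives the third almost none. The SAP's reason for splitting does not call for this, because a patient stays on the assigned dose until dose 4. No listed adverse-event table spans the three-dose course or the whole treatment phase, so the two halves are never put together.

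The practical risk is greatest for a patient who stops after dose 3. That patient never has an additional treatment visit, and an event that ended dosing is what a safety reader most wants to find in the right table. With cohorts of 3 or 6, the placement of one patient visibly changes an incidence.

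The shift tables raise a related problem. A worst-case shift is meant to show the worst status reached, but this one stops at the third of up to nine doses although ECOG is recorded at every later dosing visit.

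**Working it through.** **1. Dosing days.** Dose k falls on Day 1 + 21(k − 1). Dose 3 is 1 + 2 × 21 = Day 43, which matches the protocol. Doses 4 to 9 fall on Days 64, 85, 106, 127, 148 and 169.

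**2. What the first period contains.** The 21-day intervals are Days 1–21, 22–42 and 43–63. A cut through Day 43 keeps 21, 21 and 1 day of them. Days 44–63, or 20 of the 63 days (20/63 = 32%), move to the second period. This is time moved between tables, not time lost.

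**3. The TEAE window.** SAP 7.4.5 runs it to 30 days after the final dose.
- Three doses: 43 + 30 = Day 73, so Days 44–73 (30 days) lie outside the first-period tables.
- Nine doses: 169 + 30 = Day 199, and the first period covers 43/199 = 22% of it.

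**4. Where a Day 50 event goes if the patient stops after dose 3.** The provisions side by side:
- SAP 8.6: the second period is additional treatment visits plus the end of treatment phase visit. By SAP 7.4.5 this patient has such a visit, at about Day 43 + 28 = Day 71.
- SAP 8.6.1 (site reactions): additional treatment visits only.
- SAP 8.6.2 (adverse events): additional treatment visits and end of study.
- SAP 7.4.7: end of study is grouped with the scheduled visits, and the early-termination rule covers visits no later than Day 43.
- SAP 7.4: follow-up assessments stay out of tables unless noted otherwise.
- SAP 10.1: the tables of TEAEs leading to permanent discontinuation are 14.3.2.6.1 (through Day 43) and 14.3.2.6.2 (additional treatment visits). A Day 50 event in this patient falls after the first and is tied to no visit of the kind named in the second.

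If the event is misplaced, the incidence changes by 1/3 = 33 points in a cohort of 3, or 1/6 = 17 points in a cohort of 6.

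**5. Visits used by the shift tables in a nine-dose course.** From the time and events schedule, on treatment and after baseline:
- ECOG: Days 8, 15, 22, 43 and six later dosing visits, 10 in all. Through Day 43: 4 of 10.
- ECG: Days 22, 43 and six later dosing visits, 8 in all. Through Day 43: 2 of 8.

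The title of ECOG shift Table 14.3.5.2 carries the Day 43 limit. The title of ECG shift Table 14.3.6.2 does not, so for ECG the text and the table list disagree.

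**6. Comparison within the SAP.** PSA velocity and doubling time have summaries through Day 43, end of treatment and end of study (Tables 14.2.3.2.1 to 14.2.3.2.3). Adverse events have no such cumulative range.

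**The case against.** The best defence is that nothing is discarded. SAP 8.6 and 8.6.2 carry later data into second-period summaries, and 8.6.2 attributes each later TEAE to the dose taken at its onset, so an event between doses 3 and 4 keeps the correct dose label. The serious-event listing (14.3.2.7) has no Day 43 limit and gives time since last dose. All TEAEs are listed by subject. With about 18 patients and a descriptive analysis, a reader can reconstruct the picture. The table shells are in a separate document and may settle the titles. Any cut is partly a matter of preference.

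Most of this stands, and it rules out several stronger readings that a reader might infer:
- *All reactions to dose 3 leave the first-period tables.* They do not. Protocol 5.5.2.5 places the Day 43 site assessment after administration, so same-day reactions stay in.
- *Later events are lost.* They move to other summaries and to listings.
- *The rat data predict stronger reactions with more doses.* Protocol 3.2 links the number of doses to antibody response. It reports no local reactogenicity or adverse events with multiple doses in mice and rats, and describes the injection-site and prothrombin-time findings by dose level and as non-adverse.
- *An ECG change at doses 4 to 9 can appear in no shift table.* The unrestricted title of Table 14.3.6.2 leaves this open.

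The defence does not explain why the cut falls at dose 3 when dose changes begin at dose 4. Nor does it resolve the conflicting definitions of the second period or extend the ECOG shift. Listings do not replace an incidence table whose numerator is undefined.

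**Conclusion.** The point holds as a reporting defect that should be corrected. The assigned-dose TEAE tables omit onsets on 20 of the 21 days of the dose 3 interval. For a patient who stops after dose 3, the SAP gives no single answer on where TEAEs from Days 44 to 73 are counted. The worst-case ECOG shift uses 4 of 10 scheduled on-treatment visits in a nine-dose course. The ECG shift uses 2 of 8 if the text governs. DLT and MTD decisions use only the first 21 days and are unaffected.

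These figures assume nominal visit days and a calendar-day cut. The Day 43 visit has a window of ± 3 days, so actual counts will vary slightly. Because the Day 43 ECOG and ECG are listed ahead of dosing in protocol 5.5.2.5, one may infer that the shifts reflect only the first two dosing intervals. The protocol states pre-dose timing only for the immunologic sample, so that remains an inference, and the visit counts do not depend on it.

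**What to change.** 1. In SAP 8.6 and 8.6.2, end the first TEAE period just before dose 4, or 30 days after dose 3 if no dose 4 is given. Assign every later TEAE to the second period whether or not an additional treatment visit took place. Saying last dose instead of dose 3 would also cover a patient who stops after dose 2, whose window runs to 22 + 30 = Day 52. State how a patient who resumes after a break is handled.
2. Use one definition of the second period in SAP 7.4, 7.4.7, 8.6, 8.6.1 and 8.6.2, and retitle the paired tables to match.
3. Run the worst-case ECOG shift and the ECG interpretation shift through the end of treatment phase visit, and align the SAP 8.6.6 text with the title of Table 14.3.6.2.

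The cost is SAP wording, revised table titles and a changed date cut in programming, with no new data. One small drawback is that first-period length will differ between patients when dosing is delayed, since protocol 5.3.5.2 allows an interval of up to 42 days. Reporting days at risk beside each incidence would make this visible.
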